**Table 4. Karch and Lasagna algorithm modified by Naranjo**

## 8.5 Unanticipated Problems

Unanticipated problems (ANP) consider those situations that pose risks to the subjects.

Participants, in general, any incident, experience or outcome that meets all criteria following:

- Unexpected in terms of its nature, severity, or frequency in relation to: 1) study-related documents such as the investigator's manual, study protocol, and informed consent form; and 2) the characteristics of the study population.
- Related or possibly related to your participation in the study (possibly related means that there is a reasonable possibility that the incident or results were caused by study procedures).
- Indicative that the research places participants at increased risk of harm (including physical, psychological, economic or social) than previously recognized.

### 8.5.1 PNA Report

The PI will be responsible for reporting PNAs to the sponsor, the IC, and the IEC. The report must contain the following information:

- Study identification: protocol title and number, name of the PI and, where applicable, the center.
- Detailed description of the event, incident, experience or result.
- Explanation, justification of the reasons why the incident represents a PNA.
- Description of changes to the protocol or corrective actions taken or proposed in response to the PNA.

PNAs that are EAS must be reported to the IEC and the sponsor within the first 24 hours of that the IP was aware of this.

Any other PNA will be reported to the CEI and the sponsor within the first 5 business days after the IP became aware of this.

## 9. Study monitoring

---

The study sponsor is responsible for monitoring the study. Monitoring activities include:

but are not limited to: general safety monitoring, general study quality monitoring, monitoring by study site, detection monitoring, reporting and follow-up of adverse events, monitoring to resolve discrepancies in data capture, etc.

Responsibility for monitoring activities and ultimate responsibility for monitoring rests with the sponsor.

Details of the monitoring activities are specified in a separate document from this protocol. in a Monitoring Plan.

### 9.1 Monitoring of study centers

Monitoring of the research centers participating in the study will be carried out. For each center, At least one initial visit and one closing visit must be carried out, which does not exclude the carrying out of one or more several follow-up visits between those two mandatory visits.

The initial visit must be carried out before the inclusion of the first participant in that center; in it, the monitor will verify that the material to be used during the study has been received and that the personnel who will participate in the study activities has been trained on the study, will also verify that comply with applicable regulatory requirements and standard operating procedures.

At the follow-up visit(s), the monitor will review the study documents to confirm that: the research protocol has been followed, standard procedures have been followed applicable operating procedures, data filling has been complete and timely, and that event reports adverse events have been carried out appropriately. At this visit the monitor will discuss the findings with the researcher and will define the actions to be carried out.

The closing visit will take place at the end of the study, once the last participant from the site has been discharged from monitoring. During this visit, the monitor will verify that the site has all the documents needed to file, that all biological samples have been sent for analysis, that everything the study drug (used and unused) has been recovered and shipped to the sponsor, and that all unused material has been recovered.

Details on monitoring are set out in the corresponding plan.

## 9.2 Audit and quality control

To ensure compliance with GCP and all applicable regulatory requirements, Laboratories Sophia, SA de CV may conduct quality assurance audits. Regulatory agencies They could also conduct a regulatory review of this study.

Details of the audit process are set out separately in an Audit Plan.

### 9.2.1 Pre-study audit

Study centers included in the study will be subject to a pre-selection feasibility visit from the center, where it will be verified that they meet the minimum requirements indicated by the sponsor.

### 9.2.2 Audit during the conduct of the study

They may take place at any time before, during or after the conclusion of the study. If it is carried out any audit or inspection, the researcher and the institution must agree to allow the auditor/inspector has direct access to all relevant documents, and will allocate their time and that of their staff to the auditor/inspector to discuss the findings and any relevant issues. In the event that the If the audit has not been scheduled by the sponsor, the center must notify Laboratorios Sophia, SA of CV immediately.

## 10. Statistical analysis

---

### 10.1 Data analysis

#### 10.1.1 Statistical analysis

The statistical analysis will be performed by staff of Laboratorios Sophia, SA de CV. The program will be used SPSS statistical version 19.0 (IBM Corporation, Armonk, NY, USA).

Coding will be done using consecutive numbers. Data will be collected and sorted into an Excel spreadsheet (Microsoft® Office). The data will then be exported to the SPSS software platform. Variables will be categorized according to their nature.

#### 10.1.2 Data interpretation

The Kolmogorov-Smirnov test will be performed to determine the distribution of the results obtained. [53]

The results of the continuous quantitative variables will be presented in measures of central tendency: mean, standard deviation and ranges.

The statistical analysis of continuous quantitative variables to find significant differences ( $p$ ) will be as follows:

- Intra-group analysis: They will be determined by the Wilcoxon rank test, for the quantitative variables. [54]

The level of difference to consider significance will be an alpha ( $\alpha$ ) of 0.05 or less.

The results of the nominal and ordinal qualitative variables will be presented in frequencies, proportions and percentages.

Statistical analysis to identify significant differences in qualitative variables will be performed by creating 2x2 contingency tables and will be carried out as follows:

- Intra-group analysis: Pearson's Chi-square ( $\chi^2$ ) test or Fisher's exact test on expected values under 5.

The level of difference to consider significance will be an alpha ( $\alpha$ ) of 0.05 or less.

For adverse event reporting, all eyes of participants assigned to the intervention after the baseline visit will be considered. Results will be expressed as a percentage of subjects.

The final results report will be displayed in tables or graphs, as appropriate.

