### 4.1 Design Overview

Phase I clinical trial, controlled, non-comparative, open, single-center

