#### 7.3.2 Secondary outcome variables

- Changes in Corrected Visual Acuity (CCVA) (TE: day 8).
- Changes in corneal and conjunctival staining with lissamine green (TE: day 8).
- Corneal and conjunctival staining changes with fluorescein (TE: day 8).
- Conjunctival hyperemia changes (TE: day 8).
- Incidence of chemosis (TE: day 8).

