#### **7.3.3.4 Corneal and conjunctival staining with fluorescein**

A drop of topical anesthetic will be instilled in the conjunctival fornix, then a drop will be applied. second drop on the tip of the fluorescein strip allowing it to sit on the strip for 5 seconds to elute the dye, shaking off the excess at the end. A small contact of the strip with the conjunctiva is made in the temporal fornix, while the patient looks up, without damaging the conjunctiva. It will be classified as according to the Oxford scale.[45]

The PI will record in the file and the eCRF the grade awarded for fluorescein staining of OD and OS respectively.

Management as AE: Corneal staining that is equal to or greater than grade III will be considered as AE.

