#### **7.3.3.6 Conjunctival hyperemia**

Conjunctival hyperemia is defined as the simplest reaction of the conjunctiva to a stimulus, it is seen a red appearance secondary to vasodilation of the conjunctival vessels of varying intensity. It will be graded using the Efron scale. [46] See appendix.

Management as AE: Conjunctival hyperemias classified as grade 3 or higher will be considered as AE. superiors.

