7.0 Methods of Analysis [5]

Statistical analysis will be performed by personnel from Laboratorios Sophia, SA de CV. SPSS version 19.0 (IBM Corporation, Armonk, NY, USA) will be used. Coding will be performed using consecutive numbers. Data will be collected and organized in an Excel spreadsheet (Microsoft® Office). The data will then be exported to the SPSS platform. Variables will be categorized according to their nature (see [Table 2](#)).

Study participants will be identified by a number and their initials.

The initials of the subject of study will be obtained starting with the first letter of the name, followed by the first letter of the first surname and the first letter of the second surname, obtaining a maximum of three letters. In case the person has two names or a compound surname, the first letter will always be used.

Example:

A. [name]

B. [name]

a. Initials: AMC

b. Initials: JDO

Once the subject has been selected, they will be assigned a number that will identify them throughout the study. This code will consist of eight numbers in the following order from left to right:

- three digits of the molecule under study according to the name given by the sponsor.
- two digits corresponding to the research center number.
- three digits of the consecutive number assigned to its inclusion in the research center.

The Kolmogorov-Smirnov test will be performed to determine the distribution of the results obtained. [3]

The results of continuous quantitative variables will be presented in measures of central tendency: mean, standard deviation and ranges.

The statistical analysis of continuous quantitative variables to find significant differences (p) will be as follows:

- Intra-group analysis: They will be determined using the Wilcoxon rank test for quantitative variables. [6]

The level of difference to consider significance will be an alpha (α) of 0.05 or less.

The results of the nominal and ordinal qualitative variables will be presented in frequencies, proportions and percentages.

Statistical analysis to identify significant differences in qualitative variables will be performed by creating 2x2 contingency tables and will be carried out as follows:

- Intra-group analysis: Pearson's Chi-square (χ^2) test or Fisher's exact test for expected values less than 5.

The level of difference to consider significance will be an alpha (α) of 0.05 or less.

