For adverse event reporting, all eyes of participants assigned to the intervention after the baseline visit will be considered. Results will be expressed as a percentage of subjects.

The final results report will be displayed in tables or graphs, as appropriate.

Table 3. Triangulation of concepts [5]

| Variable type | Variable | A1 | B1 | B2 | C1 | C2 | D1 | D2 | D3 | D4 |
|--------------------------|---|----|----|----|----|----|----|----|----|----|
| Background | | | | | | | | | | |
| A1 | Demographics | | | DT | | | | | | |
| Basal | | | | | | | | | | |
| B1 | Medical record | | | DT | | | | | | |
| B2 | Comprehensive ophthalmological evaluation | | DT | | TB | | | | B | |
| Security | | | | | | | | | | |
| C1 | EAs | | | | TB | B | B | TB | TB | TB |
| C2 | ICO | | DB | | B | B | | | | |
| Secondary outcome | | | | | | | | | | |
| D1 | MAVC | | DB | | B | | B | | | |
| D2 | Ocular surface stains (TF and TVL). | DT | | | T | | | T | | |
| D3 | Conjunctival hyperemia | TD | | DT | T | | | | T | |
| D4 | Chemosis | TD | | DT | T | | | | | T |

D. Descriptive statistics; T, 2x2 contingency table; B, Bivariate analysis; M, Multivariate analysis.

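### Before-after changes in staining and hyperemia are assigned an unpaired 2x2 chi-square/Fisher test, with no cut-point for the ordinal grades

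*Protocol*

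**What the plan says.** The study has a single arm; protocol 4.1 describes it as "Phase I clinical trial, controlled, non-comparative, open, single-center". Protocol 7.3.2 lists changes in staining (both dyes) and in hyperemia at day 8 as secondary outcomes, and chemosis as an incidence. Protocol Table 3 (7.3.3) has all of them recorded at the baseline and final visits and assigns each chi-square or Fisher's exact test.

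For qualitative variables, protocol 10.1.2 states: "Statistical analysis to identify significant differences in qualitative variables will be performed by creating 2x2 contingency tables". It labels the analysis intra-group. SAP 7.0 has the same rule, with "Fisher's exact test for expected values less than 5". The triangulation table in SAP 7.0 codes stains, hyperemia and chemosis as T, under the key "T, 2x2 contingency table; B, Bivariate analysis".

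No paired test for categorical data is named. The only paired method is the Wilcoxon test (protocol reference 54 is a signed-rank article), and its use is limited: "They will be determined by the Wilcoxon rank test, for the quantitative variables".

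The only thresholds on the grades are adverse-event rules: "Corneal staining that is equal to or greater than grade III will be considered as AE" (protocol 7.3.3.4, repeated in 7.3.3.5) and "Conjunctival hyperemias classified as grade 3 or higher will be considered as AE" (7.3.3.6).

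**The concern.** With no second group, the only within-group contrast that measures change is baseline against final visit in the same people. Pearson chi-square and Fisher's exact test assume that the two rows of the table are independent samples. Here they are not.

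A 2x2 table also needs a two-level variable. The Oxford scale has six grades (0 to V) and the Efron scale five (0 to 4). Without a stated cut-point or table layout, the analyst can choose both after seeing the data, and that choice can decide significance. These signs are the objective ocular-surface findings in the first human study of this formulation, and each has its own secondary objective in protocol 3.3.

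**Working it through.** **Inputs.** From the documents: one arm (protocol 4.1), two visits (Table 3), 22 subjects (10.2.1), alpha 0.05 and the Pearson-or-Fisher rule (10.1.2). The documents give no expected frequency for any sign and no figure for this analysis to reproduce; the sample size rests on adverse-event rates. Assumed here: two-sided tests, Pearson without continuity correction, 30% positivity at both visits under no change, and correlations on a latent-normal scale.

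**1. One value per subject, visit by sign.** Let φ be the correlation between visits of the 0/1 sign. The test takes the variance of the difference in proportions as 2p(1−p)/n; the true value is 2p(1−p)(1−φ)/n. For φ above 0 the test is therefore usually conservative. Exact enumeration gives the middle column of the table below. Exact McNemar gives 0.022, 0.014 and 0.005 at latent correlation 0, 0.5 and 0.8. The scale matters: a correlation of 0.5 on the observed 0/1 scale gives 0.006 for the planned test.

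**2. Both eyes pooled as 44 independent units.** Let φ_e be the correlation between eyes, φ_v between visits in the same eye, and φ_x between one eye at baseline and the other at the final visit. The true variance is 2p(1−p)[1 + φ_e − φ_v − φ_x]/44, against 2p(1−p)/44 assumed. The test is anti-conservative when φ_e exceeds φ_v + φ_x. Two separate simulations (latent inter-eye correlation 0.8 assumed) give the right-hand column.

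| Latent visit correlation | Type I error, 22 subjects | Type I error, 44 eyes pooled |
|---|---|---|
| 0 | 0.047 | 0.12–0.13 |
| 0.3 | not computed | about 0.09 |
| 0.5 | 0.016 | 0.055–0.059 |
| 0.8 | 0.003 | 0.012–0.013 |

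**3. Pairing can change the result either way (22 subjects).**
- 4 positive at baseline, 10 at the final visit (6 new, 0 resolved). Smallest expected count (4+10)/2 = 7, so Pearson applies: 44(4×12 − 18×10)²/(22×22×14×30) = 3.77, p = 0.052. Exact McNemar: 2×0.5⁶ = 0.031.
- 0 positive at baseline, 5 at the final visit. Smallest expected count 2.5, so Fisher applies: 2×C(22,5)/C(44,5) = 0.0485. Exact McNemar: 2×0.5⁵ = 0.0625.

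**4. The cut-point decides the answer.** Suppose 4 subjects move from grade I to II, 6 from 0 to I, and 12 stay at 0.
- Cut at I or above: 4 against 10 of 22, p = 0.052.
- Cut at II or above: 0 against 4 of 22, Fisher 2×C(22,4)/C(44,4) = 0.108.
- Cut at III or above: no positives, so no test.
- Exact signed-rank on the grades: 10 worse by one grade, none better, 2×0.5¹⁰ = 0.002.

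**5. If the table were baseline by final visit.** With 16 subjects absent at both visits and 6 present at both, nobody changes, yet Fisher gives 1/C(22,6) = 0.000013. With 10 new and 1 resolved (table [[1,1],[10,10]]), Fisher gives 1.00, while exact McNemar gives 2(1+11)/2¹¹ = 0.012. This layout tests association, not change.

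**6. Power of the replacement (one value per subject, simulated, assumed grade distributions).**
- Grades 0/I/II/III moving from 80/15/4/1% to 50/30/15/5%, latent visit correlation 0, 0.5, 0.8: planned test cut at I or above 55%, 55%, 56%; exact signed-rank 49%, 65%, 85%.
- Near-zero baseline (95/4/0.9/0.1% to 75/18/6/1%), same correlations: planned 37%, 35%, 34%; exact signed-rank 26%, 30%, 36%.

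**The case against.** - **Chi-square/Fisher may be meant for crossings of different variables.** The SAP triangulation table does cross signs with adverse events, and there these tests can be suitable at subject level. But protocol Table 3 names them as the test for each sign measured at both visits, and no other before-after test is given for those signs.
- **Grade III/3 could serve as the cut-point.** It appears only as an adverse-event rule and is never tied to the analysis. The staining rule also covers the cornea only.
- **The direction of error.** A reader might infer that an unpaired test simply costs power, or that it simply inflates false positives. The documents support neither in general. Protocol 10.1.3, 10.1.4, 10.2.1 and SAP 5.0 refer to both eyes, while protocol 10.2.2 says each subject contributes one eye. The sign of the error turns on that.
- **The baseline-by-final layout.** A reader might take step 5 as the planned analysis. The plan never states a layout, and its aim of finding differences points more to visit by sign.
- **Chemosis.** It is named as an incidence and is already binary, so the cut-point issue does not arise. Subjects are clinically healthy and active inflammatory disease is excluded, so baseline should be near zero, where Fisher is more sensitive than McNemar (step 3). It is not part of the main claim.
- **Power.** A reader might expect paired tests always to detect more. Step 6 shows the gain for the grades disappearing or reversing when baseline is near zero and the visits are weakly correlated, which is plausible in healthy subjects.
- **Limited consequence.** This stands. Frequencies are reported in any case, and grade III/3 findings are handled as adverse events whatever the test shows.

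**Conclusion.** The point holds for changes in fluorescein staining, lissamine green staining and hyperemia. The assigned test is unpaired for paired data, and it dichotomises the grades without a stated cut-point. That makes the specification wrong as written rather than merely short on detail.

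Under the assumed 30% positivity, type I error runs from 0.003 to 0.047 with one value per subject, and from about 0.01 to about 0.12–0.13 with 44 pooled eyes. The sizes rest on assumed prevalences and latent correlations; the mismatch between test and design does not. What the correction buys is a valid test and no free choice of cut-point, not a guaranteed gain in power.

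It should be corrected, but it is not critical. A reader might infer that the study's safety conclusion is undermined; it is not. The rule in protocol 10.1.5 depends on unexpected related adverse events, and the comfort-index score already has a Wilcoxon test.

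**What to change.** Amend protocol Table 3 and 10.1.2, and SAP 6 and 7.0:

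1. Analyse one value per subject per visit under a fixed rule, for example the worse eye determined separately at each visit. Reconcile the both-eyes statements (protocol 10.1.4, 10.2.1; SAP 5.0) with the one-eye statement (protocol 10.2.2).
2. Test Oxford and Efron grades with the exact Wilcoxon signed-rank test, with no cut-point. Write exact explicitly: with 5 subjects worse by one grade and none better, the exact p is 0.0625 but the asymptotic p is 0.025.
3. For chemosis, report the day-8 incidence with an exact confidence interval and the counts of new and resolved cases. If a before-after test is made, use exact McNemar.
4. Keep chi-square/Fisher only for crossings of different variables, at subject level.

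The cost is wording; no new data or visits are needed. With a near-zero baseline the exact paired tests can be less sensitive than the planned test: 0 to 5 of 22 gives 0.0625 against 0.0485, and for the grades about 11 points of power can be lost (37% against 26%) if the visits are uncorrelated.

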### 10.1.4 Deviations from the statistical analysis plan

According to the sample size calculation to meet the objective of the study, 22 subjects are required. evaluable (both eyes). If this number is not met due to a loss of subjects greater than to the 20% contemplated in this protocol (loss to follow-up or withdrawal of FCI), the sponsor may replace these subjects.

The results obtained from the replaced subjects will continue to be used for the analysis of security and will be part of the ITT.

### 10.1.5 Subjects included in the analysis

Those subjects who meet an adherence  $\geq 75\%$  will be included in the statistical analysis for meet the objective of the study, taken from the weight of the PI.

The investigational drug will be considered safe and tolerable when present in less than 10% of the study population unexpected adverse events related to the investigational product.

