### 3.4 Hypothesis

#### 3.4.1 Hypothesis

H0= The PRO-172 ophthalmic solution is safe and tolerable in its ophthalmic application as it presents in less than 10% of the study population unexpected adverse events related to the investigational product.

H1= PRO-172 ophthalmic solution is not safe and tolerable for ophthalmic application as it presents more than 10% of the study population unexpected adverse events related to the investigational product.

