### 7.3 Outcome variables

#### 7.3.1 Primary outcome variables

- Incidence of unexpected AEs related to the investigational product (TE 8 and 10).
- ICO score (TE 8).

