## 10.2 Sample size calculation

### 10.2.1 Calculated N

n= 22 evaluable subjects (both eyes)

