## 11.3 Early termination of study

The study may be temporarily suspended or terminated prematurely if there is a cause sufficiently reasonable. Written notice, documenting the reason for the suspension or termination early, must be delivered by the party executing the suspension. The IP must inform as soon as possible to the study participants, the CI and the IEC, providing the reasons.

Situations in which suspension or early termination of the study will be considered include, but are not limited to:  
limit:

1. Presence of serious adverse events in more than 10% of participants in a group of study.

2. The regulatory authority (COFEPRIS) considered it due to security alerts.
3. The Sponsor determines it for its convenience or eventualities such as: support economic, manufacturing errors, etc.
4. Lower recruitment than stipulated.
5. Determination of unexpected risks to participants, which are significant or unacceptable.
6. Obtaining new relevant security information.
7. Insufficient adherence to protocol requirements.
8. The data obtained are not evaluable or are not sufficiently complete.
9. Determination that the primary objective has been achieved.
10. Determination of futility.

In case of suspension, the study can be resumed once the situations that have been corrected have been resolved. resulted in suspension; as long as this justification is sufficient for the sponsor, CI, CEI and regulatory authorities.

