3.0 Study Hypothesis

H_0 : PRO-172 ophthalmic solution is safe and tolerable in its ophthalmic application, presenting in less than 10% of the study population unexpected adverse events related to the investigational product.

H_1 : PRO-172 ophthalmic solution is not safe and tolerable for ophthalmic application, as it presented unexpected adverse events related to the investigational product in less than 10% of the study population.

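### The safe-and-tolerable rule has no seriousness term, so one related serious event, or two among 22 subjects, would still earn the label

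*Protocol*

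**What the plan says.** Protocol 10.1.5 states the verdict rule: "The investigational drug will be considered safe and tolerable when present in less than 10% of the study population unexpected adverse events". Only events attributed to PRO-172 count. Protocol 3.4.1 words the null hypothesis the same way ("as it presents in less than 10% of the study population unexpected adverse events related to the investigational product"), as does SAP 3.0 ("presenting in less than 10% of the study population unexpected adverse events related to the investigational product"). The primary safety variable in Protocol 7.3.1 and SAP 6.1 is the incidence of unexpected related events, whatever their seriousness. Protocol 10.1.2 sets the unit: "Results will be expressed as a percentage of subjects". Protocol 10.2.1 plans 22 evaluable subjects.

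Seriousness is available to the analysis. Protocol 8.3 defines it, and step 4 of 8.4.3 has the investigator record it for each event. The SAP's table of operational definitions codes frequency, intensity and causality for adverse events, but not seriousness.

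The one numerical trigger that concerns serious events is item 1 of Protocol 11.3, where suspension or early termination is to be considered: "Presence of serious adverse events in more than 10% of participants in a group of study".

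Two different populations are described. Protocol 10.1.3 and 10.1.4 keep every exposed subject, including those replaced, in the safety analysis. Protocol 10.1.5 says that subjects with adherence of at least 75% "will be included in the statistical analysis for meet the objective of the study, taken from the weight of the PI".

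**The concern.** Under the rule, a trivial unexpected sign and a life-threatening reaction each count as one subject. Nothing in the analysis plan lets a serious, drug-related event change the conclusion unless enough other subjects are also affected.

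Two further features could remove a serious event from the count:

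- **Expected terms.** Protocol 7.3.3.1 lists the expected events by name only (eye irritation and dry eye among them), with no severity limit. A serious case under a listed name could be classed as expected and count as zero. Protocol 8.5 does tie unexpectedness to severity, but only for unanticipated problems.
- **Adherence filter.** Protocol 5.2 allows elimination after a serious event. Four applications a day for 7 days is 28, and 75% of 28 is 21. A subject who stops before about the 21st application would nominally fall below the cut-off and could leave the analysis described in 10.1.5.

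Protocol 2.3.2 says that this formulation has not been given to humans before. A pre-specified favourable label that can coexist with related serious harm in healthy volunteers would be a misleading summary of the trial.

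**Working it through.** **The planned number.** Protocol 10.2.2 and SAP 5.1 raise 18 by 20%: 18 × 1.2 = 21.6, rounded up to 22. The 18 can be reproduced with the stated formula at one-sided α = 0.05 and 80% power, taking p = 0.30, p₀ = 0.475 and δ = +0.10: 0.30 × 0.70 × ((1.645 + 0.842)/(−0.275))² = 17.17, rounded up to 18. The documents do not say which rates are p and p₀, and other assignments also give 18. This does not matter here. Only the range of 18 to 22 analysed subjects is used below.

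**The rule by number analysed.** The label is given when x/N < 10%.

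| N analysed | x = 1 | x = 2 | x = 3 | Largest x that passes |
|---|---|---|---|---|
| 22 | 4.5% | 9.1% | 13.6% | 2 |
| 21 | 4.8% | 9.5% | 14.3% | 2 |
| 20 | 5.0% | 10.0% | 15.0% | 1 |
| 19 | 5.3% | 10.5% | 15.8% | 1 |
| 18 | 5.6% | 11.1% | 16.7% | 1 |

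One affected subject passes when 1/N < 0.10, that is, N of 11 or more. Two pass when 2/N < 0.10, that is, N of 21 or more. The trigger in Protocol 11.3 item 1 needs more than 10%, so 2/22 does not reach it.

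**Illustration.** The documents give no rate of serious events for this product. Assume, only to show how the rule behaves, that each subject independently has a 5% chance of an unexpected, related serious event, and that no other unexpected related events occur.

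For N = 22:

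- At least one such event: 1 − 0.95²² = 0.676.
- Rule passes: P(X ≤ 2) = 0.3235 + 0.3746 + 0.2070 = 0.905.
- Both, that is, at least one serious event and the label still given: 0.3746 + 0.2070 = 0.58.

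For N = 18, 19 and 20, where only one affected subject is allowed:

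- Rule passes: P(X ≤ 1) = 0.774, 0.755 and 0.736.
- Both: P(X = 1) = 0.38 in each case.

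If non-serious unexpected related events also occurred in other subjects, the chance of passing would be lower. The pass figures are therefore upper values for the assumed rate.

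**Do other provisions reach the verdict?**

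| Provision | What it governs | Changes the 10.1.5 label? |
|---|---|---|
| 5.2, elimination after a serious event | The individual subject | No |
| 8.4.3 and 8.5.1, 24-hour reporting | Notification | No |
| 11.3 item 1, more than 10% with serious events | Consideration of suspension or termination | No; not reached by 2/22 |
| 11.3 items 2, 5 and 6 (regulator, unacceptable unexpected risks, new safety information) | Suspension or termination, by judgement | No |

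**The case against.** The strongest reply is that the protocol does not ignore serious events. The list in 11.3 is expressly open-ended. Two unexpected, drug-related serious events in healthy volunteers would fit item 5 at any percentage, and items 2 and 6 are also available. Such events go to the sponsor and the ethics committee quickly, and Protocol 8.4 and 13.1 put adverse events into a final report that follows ICH E3. All of this stands. A reader might infer from item 1 that 10% is the only safeguard, or that serious events could go unreported; the documents support neither reading. What remains is narrower: those provisions govern conduct and reporting, and leave the pre-specified conclusion untouched.

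Other stronger readings also fail:

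- **That the label is a formal gate to phase II.** Protocol 6.1.3.1 says only that four-times-daily safety is studied with a view to evaluating a higher dosage in phase II. No passage makes the label a go/no-go condition.
- **That two serious events always pass.** They fail once 20 or fewer subjects are analysed, which is within the loss allowance. One event still passes.
- **That 5% is a forecast.** Protocol 2.2.3 reports no serious events in healthy people using the drops twice daily for 6 weeks, though that is a different regimen. A true rate of 10% would be less informative still. At N = 22 the chance of at least one event is then 0.902 and of passing 0.620, but 10% is the rule's own threshold, so this shows small-sample behaviour for any kind of event.

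It is also fair to say that the criterion is applied consistently across the documents, and that requiring no related serious events is a convention they do not oblige the sponsor to adopt.

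**Conclusion.** The point holds as a gap in the decision rule. The safe-and-tolerable conclusion depends only on how many subjects have an unexpected related event. One related serious event is compatible with the label at any analysed number of 11 or more, and two are compatible at 21 or more. A serious event under a listed expected term might not count at all.

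The table of proportions follows directly from 10.1.5 and needs no assumption beyond the number analysed. The probabilities (68% with at least one event, 91% passing and 58% with both at N = 22; 74% to 77% passing at 18 to 20) rest on an assumed 5% rate and the absence of other unexpected related events. They illustrate the rule and do not predict the trial.

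This is a should-fix. No figure in the plan is wrong on this point and no passage forbids the present rule. But the rule permits a conclusion that would misdescribe the data, and it can be repaired before the results are seen.

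**What to change.** In the synopsis, Protocol 3.4 and 10.1.5, and SAP 3.0, add a second requirement for the safe-and-tolerable conclusion: no serious adverse event related to PRO-172 occurred, whether expected or not. If one occurs, report it and do not apply the label.

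Two definitions should go with it:

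- **Related.** Use the SAP's causality category of probably or possibly related. State that events judged certain under Protocol 8.3 belong there too, since the SAP coding has no separate value for them.
- **Population.** Assess this condition in all exposed subjects, the safety population of Protocol 10.1.3, and not only in those with adherence of at least 75%. This is a deliberate choice of denominator for the new condition and should be written down as such.

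The SAP's adverse event coding should gain a seriousness item so that the condition can be evaluated. While SAP 3.0 is open, its alternative hypothesis, which also says less than 10%, needs correcting as a separate matter.

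The cost is a protocol amendment with its committee and regulatory approvals under Protocol 11.2. There is also a real downside: in an uncontrolled study, a single serious event judged possibly related removes the label even if another cause is plausible. No extra subjects or visits are needed, and no change to stopping, elimination or treatment rules is proposed.
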